7.2.3. Vital Signs, Physical Examination, and ECG

Assessment of vital signs (supine blood pressure, heart rate, and body temperature), physical examination and ECG will be performed at the time points indicated in the General Schedule of Assessments for Part A ([Table 1](#)) and for Part B ([Table 2](#)) (predose at dosing days).

Supine blood pressure and heart rate will be measured using standard equipment after 10 minutes rest on a bed.

It is recommended that the method used to measure body temperature at SEB is maintained throughout the trial for each patient.

A physical examination will include at a minimum an assessment of general appearance, skin, lymph nodes, musculoskeletal/extremities, abdomen, cardiovascular, respiratory, and neurological system.

Weight will be measured at SEB, at the EoA/ED visit, at visit 1 of Part B, at the EoS/ED visit, and can be repeated at any visit when there is an obvious weight change compared to the last weight assessment. Patients will be required to remove their shoes and wear light indoor clothing for this measurement.

A 12-lead ECG will be recorded locally as per local regulations in the supine position after the patient has rested in this position for at least 10 minutes. The assessments on heart rate, PR, QT and QRS intervals will be read centrally.

7.2.4. Suicidality Assessment

As is recommended for trials involving a biological product for a neurological indication, a prospective assessment for suicidal ideation and behavior will be included in this clinical trial (Part A only).

This so-called suicidality assessment will be conducted by specifically asking the following question, derived from the PHQ-9:

- "Over the last 2 weeks, how often have you been bothered by thoughts that you would be better off dead, or of hurting yourself in some way?"

The patient will be asked this question at each visit and the response documented. Response options as per the PHQ-9 are limited to the following: "*not at all*," "*several days*," "*more than half the days*" or "*nearly every day*."

This specific question was selected for the reported significant linear relationship between the item 9 score of the PHQ-9 and the risk of subsequent suicide attempt.¹⁷

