- ^q Samples for anti-drug antibodies (ADAs) will be collected predose on dosing days.
- ^r Efgartigimod will be administered as an intravenous (IV) infusion over a period of 1 hour at visits 1, 2, 3, and 4 of each treatment period. Patients will remain at the site for at least 1 hour following the end of the infusion for safety monitoring based on the patient's clinical status. At TPnV1, the conditions for (re-)treatment will be checked before administration of efgartigimod.
- ^s Clinically relevant prior treatment will only be recorded at SEB. All available vaccination history will be recorded as part of the participant's prior medication for vaccinations received in the past or concomitant medication for vaccinations received during the trial. For vaccines where multiple doses or boosters are received, only the most recent one must be recorded.
- * Assessments highlighted by use of bold italics indicate assessments that may be carried out as a telephone assessment visit under the conditions outlined in Appendix 8.

Figure 1: ARGX-113-1705 Trial Design for Part A

Roll-over from trial ARGX-113-1704

ED = Early Discontinuation; EoA = End of Part A; ITP_n Vn = Inter Treatment Period_(number) Visit in Part A; TP_n B = Treatment Period_(number) Baseline in Part A; TP_n Vn = Treatment Period_(number) Visit in Part A; SEB = Study Entry baseline; SoC = Standard of Care
Patients will be dosed on an "as needed basis".

Note: All available vaccination history will be captured as part of the participant's prior medication for vaccinations received in the past or concomitant medication for vaccinations received during the trial as described in the General Schedule of Assessments for Part A (Table 1).

^a Weekly visits (window ±1 day) during the Treatment Periods

^b Visits every 30 days (window ±2 days) during the Inter Treatment Periods. The length between Treatment Periods may vary for each patient.

^c EoA visit (window ± 7 days).

Table 2 General Schedule of Assessments for Part B

Assessment	Treatment Period				Intertreatment Period ^{a, b}	End of Study ^c /Early Discontinuation ^{d, e}	Unscheduled ^f
	TPE _n V1 ^g (TPE _n B)	TPE _n V2 (X+7)±1	TPE _n V3 (X+14)±1	TPE _n V4 (X+21)±1			
Visits Subsequent Treatment Periods	X				ITPE _n Vn ^g	EoS/ED	UNS
Trial Day (Visit Windows)					Y+90 (±7)	1095±7	
*MG-ADL ^h	X	X	X	X		X	X
Physical examination						X	X
Weight ⁱ	X					X	X
Vital signs ^j	X	X	X	X	X	X	X
ECG ^k	X				X	X	X
Clinical laboratory tests ^l	X					X	X

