Additionally, any case of infection is regarded as an adverse event of special interest (AESI) and is subject to structured safety reporting with standardized questions in the eCRF.

The current COVID-19 situation warrants new measures to be introduced for patient safety. These measures will allow patients to be evaluated remotely if/when quarantine is imposed. For example, any remaining visits in an interrupted Treatment Period, may be performed remotely, in cases where the patient is not allowed or cannot physically visit the site. These measures respect both patient safety and local guidance, as well as allowing basic safety data to be collected.

The assessments identified for telephone assessment visits are highlighted with the use of bold italics in the existing Schedule of Assessments for Part A in [Table 1](#) and for Part B in [Table 2](#). Guidance on the execution of these visits and assessments is given below.

By providing a structured back-up plan, we aim to mitigate the risks of the COVID-19 pandemic, while still respecting both patient safety and collection of safety data and remaining compliant with GCP.

Visits with the possibility of remote assessment by telephone:

TP_xV2, TPE_xV2, TP_xV3, TPE_xV3, TP_xV4, TPE_xV4, ITP_xV_x, ITPE_xV_x, EoA, EoS, ED, and UNS. See the Schedule of Assessments for Part A ([Table 1](#)) and for Part B ([Table 2](#)).

Treatment Period visits will be replaced by telephone assessment visits during the current COVID-19 situation when the Treatment Period is considered interrupted.

Mandatory physical visits:

Initiating a new Treatment Period can only be done when the patient is physically on site.

Guidance to Sites in Case of Suspected COVID-19 in Patients

As sponsor we want to emphasize and highlight the need to follow the guidance issued by local authorities. Wherever guidance is unclear, or if no specific guidance is available, argenx will recommend to either postpone the visit if possible or evaluate the need for telephone assessments to replace a physical visit.

The site should contact the patient prior to each visit, and conduct the following COVID-19 assessments:

1. Does the patient have symptoms, such as cough, fever, muscle pain, shortness of breath*?

- If NO: Go to Questions 2 and 3.

- If YES:

- The patient should be tested for COVID-19:

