- If the contact was 14 days or longer before the study visit => the visit can go ahead as planned. If the patient cannot physically come to the clinic due to the local COVID-19 situation, the visit can be replaced by a telephone assessment visit.
- If the contact was less than 14 days before the study visit => the visit needs to be rescheduled at least 14 days after the contact occurred or be replaced by a telephone assessment visit.

How to: Information related to study procedures and data collection

The assessments deemed suitable for telephone consultation are:

- Re-consenting where warranted, MG-ADL, Adverse Event and Concomitant Medication questioning.

Since QMG needs quantification by the physician, using specific equipment, such as a dynamometer and spirometer, this assessment is not deemed suitable for telephone assessment.

Telephone consultation will allow safety data to be collected and to check on the patient's well-being, while the derived MG-ADL score may give an indication of the need for another treatment with efgartigimod.

Re-consenting with the updated ICF, or consent to Part B of the ADAPT+ study can be done remotely in view of the COVID-19 situation.

Options for consent might entail:

- physical signature by sending the ICF to the patient by courier and having a phone call with the patient, then having the signed document sent back to the site.
- phone call with the patient, asking for email confirmation to corroborate verbal consent.
- organize a conference call or video call together with the patient and impartial witness, where needed.
- if no phone call or video call is possible, email documented consent.

Depending on regional requirements the options can be limited, after consultation with the relevant IRB/IEC and/or regulatory authority.

Data collected during a telephone assessment visit can be entered into the e-CRF pages of the corresponding "missed" visit. Enter the date of the phone call as the "date of visit" and enter the data obtained in the applicable CRF pages. For the assessments that are not performed, answer "no" to the question if the assessment was made in the respective forms. Add "COVID-19 telephone" in the comment section of the CRF.

If you are not able to contact the patient, inactivate the full study visit in the CRF and confirm the missing visit in the comments section as “COVID-19.”

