5.5.2 Presentation of results

Suicidality assessment results will be presented using a frequency tabulation by analysis visit and worst over time. The denominator for the percentage is the total number of patients per treatment and analysis visit in the safety analysis set.

All suicidality assessment data will be listed, but only for patients with any post-baseline category ≥ 1 .

	
Statistical Analysis Plan
	

ARGX-113-1705
	
Final Analysis
	
Final 1.0 of 20SEP2022

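### The suicidality question is required at every Part A visit but is left off the telephone-visit list without a reason, and no planned summary table shows new or worsened ideation

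*Protocol*

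**What the plan says.** Protocol Section 7.2.4 plans a prospective suicidality assessment, in Part A only, by one question taken from the PHQ-9: "Over the last 2 weeks, how often have you been bothered by thoughts that you would be better off dead" (the item goes on to self-harm). There are four possible answers. On frequency it says: "The patient will be asked this question at each visit and the response documented". Table 1 schedules the assessment at every Part A visit.

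Appendix 8 sets temporary COVID-19 procedures. It allows visits 2 to 4 of a treatment period, intertreatment (ITP), end of Part A, early discontinuation and unscheduled visits to be held by telephone; the treatment-period visits move to telephone when the period counts as interrupted. The assessments it considers suitable by telephone are: "Re-consenting where warranted, MG-ADL, Adverse Event and Concomitant Medication questioning". For QMG it explains that equipment is needed and concludes that "this assessment is not deemed suitable for telephone assessment". Sites record assessments that were not performed by answering no in the eCRF.

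The key to Table 1 says: "Assessments highlighted by use of bold italics indicate assessments that may be carried out as a telephone assessment visit". The marked rows are consent, MG-ADL, prior/concomitant/rescue therapy and adverse events. The suicidality row is not marked.

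On analysis, SAP 5.5.2 says: "Suicidality assessment results will be presented using a frequency tabulation by analysis visit and worst over time". It also lists all suicidality data for any patient with a post-baseline answer of 1 or more (Listing 16.2.11.1).

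**The concern.** The protocol wants a specific question asked at every visit, and Section 7.2.4 says why this one was chosen: its score is reported to relate to the risk of a later suicide attempt. The telephone procedures then drop it silently. QMG is left out for a stated practical reason that cannot apply to a spoken question, and the longer, eight-item MG-ADL is kept. The omission appears in both Appendix 8 and Table 1, so a site following either would not ask.

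The second part concerns what can be read from the results. Frequencies at each visit show how many patients gave each answer, but not whether they are the same patients as at baseline. For a safety item, the useful quantity is the number of patients whose answer became worse after dosing started, and no planned table gives it.

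**Working it through.** **Telephone visits: the passages side by side**

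| Source | Suicidality question |
|---|---|
| Protocol 7.2.4 | Asked at each visit (Part A) |
| Protocol Table 1, schedule | Planned at every Part A visit |
| Protocol Table 1, telephone marking | Not marked |
| Protocol Appendix 8, telephone list | Not listed; no reason given |

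The documents state no figure that could be reproduced here.

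**Time covered by the question**

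Inputs: recall of 2 weeks = 14 days (protocol 7.2.4); Part A ITP visits every 30 days (protocol 5.3). Visits are taken to fall exactly on schedule.

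Coverage = recall / days between two askings.

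- Every ITP visit on site: 14/30 = 47%.
- One ITP visit by telephone, question not asked: 14/60 = 23%.
- Two in a row: 14/90 = 16%.

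Coverage is therefore incomplete even with perfect attendance. One skipped asking halves it.

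**What the planned suicidality table can show**

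1. SAP 2.2.4 makes the cycle baseline (CnB) an analysis visit, and SAP 2.2.2 states that baseline coincides with C1B. The baseline distribution is therefore tabulated.
2. The table gives marginal counts only. With n patients, k0 positive at baseline and k1 positive later, the number newly positive lies between max(0, k1 − k0) and min(k1, n − k0). With assumed counts n = 100, k0 = 5, k1 = 5, the range is max(0, 0) = 0 to min(5, 95) = 5. The same table fits no new cases or five.
3. The listing resolves this. Any patient whose category rose must have a post-baseline answer of 1 or more, so every such patient is listed with all answers. The count has to be made by hand.
4. SAP 5.2.3, 5.3.3 and 5.4.3 plan cross-tabulations against baseline and treatment-emergent counts for laboratory, vital-sign and ECG abnormalities. SAP 5.5.2 plans neither.
5. The worst value in SAP 5.5.2 is not defined. The worst-case rule in SAP 2.2.5 is post-baseline, but applies to parameters with abnormality or toxicity grades, and SAP 5.5 defines none. If baseline were included, a patient positive only before the first dose would enter the worst row.
6. The denominator in SAP 5.5.2 is all patients per treatment and analysis visit. For laboratory and ECG abnormalities it is patients with data for the parameter. SAP 2.4.1 says missing values never enter denominators. If SAP 5.5.2 were followed literally, questions skipped at telephone visits could dilute the percentages.

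**The case against.** The strongest reply is that both gaps are limited and visible. Telephone visits are a temporary measure, and no infusion is given at one. Adverse-event questioning continues by telephone, and nothing forbids asking the suicidality question there. Missed assessments can be traced through the eCRF entries and COVID-labelled deviations, and SAP Table 14.1.1.4 counts missed and telephone visits. Suicidality is not named in the primary or secondary endpoints (protocol 3.1 and 3.2), whereas laboratory, vital-sign and ECG assessments are, so a lighter display may be proportionate. With few positive answers, a listing is a legitimate way to find new cases.

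Much of this stands. It rules out two stronger readings that a reader might infer:

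- *That some patients are followed only by telephone, so that monitoring is switched off for them.* Appendix 8 says: "Initiating a new Treatment Period can only be done when the patient is physically on site". Every treatment period therefore begins with an on-site visit at which the question is scheduled. The gap belongs to visits held by telephone, not to a group of patients.
- *That the baseline answer is not tabulated, so new ideation cannot be told from old.* C1B is an analysis visit, and the listing gives each relevant patient's full series of answers.

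Two things remain unanswered. The adverse-event prompt in Section 7.2.1.2 is an open question about health problems and does not replace a targeted question chosen for its link to suicide attempts. Traceability shows that an answer is missing; it does not supply it.

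**Conclusion.** The point holds as a modest, inexpensive improvement to safety monitoring and reporting.

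The requirement in Section 7.2.4 is inconsistent with Appendix 8 and the Table 1 markings, and the omission is unexplained. Each skipped ITP asking widens an already partial window: from 47% of the time to 23%, then to 16% after two. These figures rest on the 14-day recall, exact 30-day spacing and the question not being asked by telephone. They describe a patient to whom this happens. The documents do not say how often visits were held by telephone, so the effect on the trial as a whole cannot be sized.

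On the analysis side, new or worsened ideation appears in no summary table, though the listing allows it to be counted. The 0-to-5 range is an illustration on assumed counts. A comparison with the 1705 baseline also has limits. Some patients already received efgartigimod in 1704, and a Week 1 answer on day 8 looks back 14 days, about 7 of them before the first infusion. A cross-tabulation removes neither limit.

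**What to change.** **Protocol.** Add the suicidality question to the Appendix 8 list of telephone assessments and give its row in Table 1 (Part A) the telephone marking. This can go into the next amendment. Under Section 4.5 it needs ethics committee and, where local rules require, regulatory approval, so it costs more than the one-line edit suggests. At site level it adds one question to a call already being made. If Part A visits are complete by then, only the SAP change still has an effect.

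**SAP 5.5.2.** Define worst as worst post-baseline. Cross-tabulate it against the baseline response among patients with an answer, and report the number whose category increased. This is one more table from data already collected, in a format the SAP already uses for other safety data.

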7.2.5. Medical and Surgical History

Clinically significant findings and pre-existing conditions present in a patient prior to SEB must be reported on the relevant medical history/current medical conditions page of the eCRF.

Information should be provided on medical and surgical history, and concomitant medical conditions specifying those ongoing at SEB.

7.2.6. Data Safety Monitoring Board (DSMB)

The sponsor will appoint a DSMB consisting of an independent group of clinical experts, who are not participating in the trial. They will be supplemented by an independent statistician. The objective of the DSMB will be to review all safety data (including the overall number of patients treated up to that point, rates, and patient-level details). Fixed meetings will be scheduled based on the recruitment rate into the trial, and incidence of (S)AEs. In addition, ad hoc meetings can be requested at any time during the trial by either the sponsor or the DSMB. The DSMB will advise the sponsor concerning continuation, modification or termination of the trial after every meeting.

The composition, objectives, and role and responsibilities of the independent DSMB will be described in a DSMB charter, agreed with the DSMB members and sponsor. The DSMB charter will also define and document the content of the safety summaries, and general procedures (including communications).

7.2.7. Visit Reminder/Subject ID Card

Patients must be provided with the address and telephone number of the main contact for information about the clinical trial. The investigator must therefore provide a "Visit Reminder/Subject ID Card" to each patient. In an emergency situation this card serves to inform the responsible attending physician that the patient is in a clinical trial and that relevant information may be obtained by contacting the investigator. Patients must be instructed to keep the card in their possession at all times.

7.3. Pharmacodynamics

In Part A, the PD markers (total IgG and IgG subtypes [IgG1, IgG2, IgG3 and IgG4], and autoantibodies [anti-AChR antibodies for the AChR-Ab seropositive patients and anti-MuSK antibodies for the MuSK-Ab seropositive patients]) will be measured at the time points as indicated in [Table 1](#). Information on the AChR/MuSK-Ab serotype is available from trial ARGX-113-1704.

These PD markers will be determined using validated assays. The actual date and time of collection of the blood sample will be recorded in the relevant section of the eCRF.

7.4. Anti-Drug Antibodies

Blood samples to assess ADA will be collected predose at the time points as indicated in [Table 1](#) and [Table 2](#). At baseline (SEB, TP_nB, and TPE_nB), confirmatory and titer analysis will be performed using a validated ADA assay. Samples having a positive ADA titer will be further investigated in a neutralizing ADA assay. The actual date and time of collection of the blood sample will be recorded in the relevant section of the eCRF.

8. STATISTICS

The statistical analyses will be performed by sponsor's designated CRO using statistical analysis systems SAS® (SAS Institute, Cary, NC, United States [US]) version 9.2 or higher, and the software package R, if applicable. The standard operating procedures (SOPs) and work instructions of sponsor's designated CRO will be used as the default methodology if not otherwise specified.

Any change to the data analysis methods described underneath will be mentioned in the statistical analysis plan (SAP). Any additional analysis, and the justification for making the change, will be described in the Clinical Trial Report (CTR). Additional exploratory analyses of the data will be conducted as deemed appropriate.

Due to the single-arm, open-label nature of the design, evaluation of all endpoints will be essentially descriptive. Endpoints will be summarized by treatment (as received in ARGX-113-1704).

8.1. Determination of Sample Size

Not applicable.

8.2. Analysis Populations

The analysis population will consist of all patients who rolled over from trial ARGX-113-1704.

8.3. Patient Disposition, Characteristics and Concomitant Medication

A tabular presentation of the patient disposition will be provided. It will include the number of patients enrolled, completed (by cycle), as well as the number of early discontinuations (including rescued patients), with reasons for discontinuation from trial treatment or trial and major protocol deviations.

A listing will be presented to describe dates of SEB, completion or early discontinuation and the reason for early discontinuation, if applicable, for each patient.

Patient characteristics will be recorded prior to enrollment and will be listed and summarized. Overall summaries will include descriptive statistics for continuous measures (number of observations, mean, standard deviation, median, minimum and maximum) and for categorical measures (sample size, frequency, and percent). Patient characteristics include but are not limited to age, sex, race, weight, and body mass index (BMI).

Use of concomitant medication will be summarized with frequency and percentage. All concomitant medications used will be listed.

8.4. Statistical Methods

8.4.1. Primary and Secondary Endpoint Analyses

All endpoints will be summarized in all enrolled patients and by means of descriptive statistics. Frequency tables will be made for all binary variables, ie, AEs, by cycle and overall.

Summary statistics will be provided for the continuous endpoints (eg, laboratory values, vital signs, ECGs) in terms of absolute values and changes from TP₁B by cycle and available time points.

